Executive functions, anxiety and their relation to social participation and quality of life among children with Migraine during COVID-19

Background:

Headaches are a frequent occurrence in children and adolescents, making them the most commonly reported pain complaint when seeking medical attention. (Genizi 2013) The prevalence of migraine shows an increase from 3% during the preschool years to 23% during high school years. (Al-Twajiri 2002) The COVID-19 pandemic has profoundly affected the well-being of children and adolescents, impacting various facets of their physical and mental health. Disrupted routines, prolonged periods of social isolation, increased screen time, and heightened stress and anxiety related to the pandemic have raised concerns about the potential amplification in frequency and severity of childhood migraines. Numerous studies have documented an upsurge in migraine symptoms and frequency among children during the pandemic.(Bonuccelli 2023, Dedeoglu 2023 Caronna 2023) Factors such as changes in sleep patterns, dietary habits, physical activity levels, and emotional stress contribute to the worsening of migraine in this population. (Powers 2003, Riva 2006) Additionally, restricted access to healthcare services and disrupted follow-up care during the pandemic pose challenges for the management and treatment of childhood migraine. (Apetti 2020, Verhagen 2021, Reyes-Alvarez 2023) It is imperative for healthcare professionals to acknowledge these difficulties and provide appropriate support and interventions to mitigate the pandemic's impact on children with migraine. Future research should delve into the underlying mechanisms connecting pandemic-related

factors to the exacerbation of migraine, enabling the development of targeted strategies for prevention and management.

Our study aimed to explore COVID-19 pandemic on the executive functions (EF) , and quality of life of children with migraine and healthy controls .

We compared EF between children with migraine and healthy controls. Then, both groups were further divided to children who were affected by COVID-19 those who were not affected by COVID-19. Comparisons within and between groups of EF, anxiety, participation and QOL were performed. Among children with migraine, we examined the implications of COVID-19 restrictions on EF; we examined the correlations between EF, anxiety, participation and QOL. Based on the correlations results, we examined whether EF, anxiety, migraine severity and participation predicted QOL.

Research Objective:

Our hypotheses were that: (1) children with migraine would have significantly lower EF, higher anxiety, lower participation and QOL than healthy controls. (2) When comparing children affected by COVID-19 those who were not affected by COVID-19 within and between groups: children with migraine who were affected by COVID-19 would have the lowest EF, highest anxiety, lowest participation and QOL. (3) Among children with migraine: significant correlations would be found between migraine severity (Ped MIDAS), EF, anxiety, participation and QOL; (4) EF, anxiety, migraine severity and participation would significantly predict QOL.

Study Population:

The research will include 75 children between the ages of 6 and 18 years, diagnosed with Migraine, who are under follow-up at the Pediatric Neurology Clinic in Bnei Zion.

A control group of 75 children without Migraine, headache or other chronic diseases, assessed during routine visits at the Pediatric Neurology Clinic or for other reasons, will also be included.

Research Methods:

For the study group only:

Medical Assessment: A prospective medical history including a thorough headache history and physical and neurological assessment by a pediatric neurologist, were done in all children, during the visit at the pediatric neurology clinic. All children met the diagnostic criteria for migraine, according to the International Classification of Headache Disorders, 3rd edition (ICHD-3) (++).

PedMIDAS: Headache related disability was evaluated by the PedMIDAS questionnaire. It was developed to assess migraine disability in pediatric and adolescent patients and has been tested and validated for ages 4 to 18 (++).

For all participants:

Health status questionnaire- A thorough questionnaire about the general health of all participants, including information about COVID-19 – as whether the child was infected by the virus.

Behavior Rating Inventory of Executive Functions (BRIEF) - The BRIEF is a behavioral rating measure for children and youth aged 5-18 years, that aims to

measure the child's EF as expressed in daily life situations (for example: "becomes upset with new situations"; "has a messy desk"; "disturbed by change of teacher or class"; "does not check work for mistakes"; "has trouble concentrating on chores, schoolwork"). In the present study we used the BRIEF parents' report. The BRIEF includes 86 items that measure various EF and are summarized into two scales: Behavioral Regulation Index (BRI) (which includes the inhibition, shifting and emotional control scales), and the Metacognition Index (MI) (which includes the initiation, working memory, planning, organization of materials and monitoring scales). The Global Executive Composite (GEC) total score is generated from both BRI and MI scores. Parents rate how frequent the child express the behavior described in each BRIEF item on a Likert scale that ranges from 1 (infrequently) to 3 (often). All raw scores are converted to a standard scores. A total cut-off standard score of 65 indicates deficiencies in executive functions. As higher is the scores, the worse are the EF. The BRIEF has good psychometric properties (Gioia et al., 2015; Gioia, Isquith, Guy, & Kenworthy, 2000; McGill & Snow, 2021).

The State-Trait Anxiety Inventory for Children (STAIC) (Spielberger, C. D., Edwards, C. D., Montouri, J., & Lushene, R. (1973) distinguishes between a general proneness to anxious behavior rooted in the personality and anxiety as a fleeting emotional state. The STAIC S-Anxiety scale consists of twenty statements that ask children how they feel at a particular moment in time. The STAIC T-Anxiety scale also consists of 20 item statements, but subjects respond to these items by indicating how they generally feel. The instrument is designed to be used with upper elementary or junior high school aged children. Higher mean score represents lower anxiety.

The Child and Adolescent Scale of Participation (CASP) (Bedell, 2011) - measures the extent to which children participate in home, school, and community activities

compared to children of the same age as reported by family caregivers. The content and methods used in the CASP and CFFS were informed by the International Classification of Functioning (ICF, WHO, 2001), research addressing participation of children / youth with a range of disabilities and factors related to the child, family and physical and social environment that support and or hinder participation. The CASP consists of 20 ordinal-scaled items and four subsections: 1) Home Participation (6 items), 2) Community Participation (4 items), 3) School Participation (5 items), and 4) Home and Community Living Activities (5 items). The 20 items are rated on a four-point scale: “Age Expected (Full participation),” “Somewhat Restricted,” “Very Restricted,” “Unable.” A “Not Applicable” response is selected when the item reflects an activity in which the child would not be expected to participate due to age (e.g., work). Most items are applicable to children who are five and older. Higher scores reflect greater age-expected participation. The CASP has reported evidence of test re-test reliability (Intraclass Correlation Coefficient = 0.94), internal consistency ($\alpha \geq 0.96$) and construct and discriminant validity.

The Pediatric Quality of Life Inventory (PedsQL) (++) - We used Version 4.0 the child’s report, which profiles children’s Health-Related Quality of Life (HRQoL) in four dimensions: (1) Physical Functioning (eight items), (2) Emotional Functioning (five items), (3) Social Functioning (five items) and (4) School Functioning (five items). A higher order dimension of the Psychosocial Health dimension encompasses emotional and social functioning. The child marks the frequency of problems which occurred in the past one month on a five-point response Likert scale (0 = never a problem; 1 = almost never a problem; 2 = sometimes a problem; 3 = often a problem; 4 = almost always a problem). Items are then transformed into a 0-100-point scale (0

= 100; 1 = 75; 2 = 50; 3 = 25; 4 = 0) to present the HRQoL percentage. A higher percentage indicates a better HRQoL.

Inclusion Criteria:

Children between the ages of 6 and 18 years with Migraine.

Exclusion Criteria:

Children unable or unwilling to complete the questionnaires, and those with secondary headaches or other chronic illness.

Informed Consent:

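### The migraine-control comparison for hypothesis 1 is described without regard to COVID-19 status, and no single adjusted estimate is given beside it; a possible, unquantified bias that data already collected can address

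*Protocol*

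**What the plan says.** The paragraph just before Research Objective describes the analysis in order. It starts with executive function (EF) alone and no COVID-19 term, and only then divides both groups by COVID-19 status: "We compared EF between children with migraine and healthy controls. Then, both groups were further divided to children who were affected by COVID-19". The next step covers four domains: "Comparisons within and between groups of EF, anxiety, participation and QOL were performed".

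Under Research Objective, hypothesis 1 is the overall group difference in all four domains: "children with migraine would have significantly lower EF, higher anxiety, lower participation and QOL than healthy controls". COVID-19 status enters with hypothesis 2, which expects that "children with migraine who were affected by COVID-19 would have the lowest EF, highest anxiety, lowest participation and QOL".

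Under Study Population, the migraine group is 75 children in follow-up at the neurology clinic. The other group is "A control group of 75 children without Migraine, headache or other chronic diseases, assessed during routine visits"; that sentence goes on to name the same clinic, or other reasons for attending. No matching is stated. Under Research Methods, the health questionnaire given to all participants records whether the child was infected.

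**The concern.** Hypothesis 2 treats COVID-19 status as relevant to the same four domains on which hypothesis 1 is judged. Nothing in the design makes the infected share equal in the two groups. If COVID-19 worsens these outcomes and one group contains systematically more infected children, part of the undivided difference reflects the mix of infected and uninfected children rather than migraine. Hypothesis 1 could then look confirmed, or be missed, partly for that reason.

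The subgroup comparisons do not fully settle this. Hypothesis 2 is a prediction about which of four cells is worst. It does not combine the two strata into one migraine-control contrast, and each stratum alone has much less precision than the whole sample.

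**Working it through.** The Protocol states no significance level, power, SD, infected share or COVID-19 effect, so there is no figure of its own to reproduce.

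**Inputs**
- From Study Population: 75 children per group.
- Assumed: two-sided 5% test, normal approximation, SD 1 within each migraine-by-infection cell, shares centred on 50%, the same COVID-19 effect *d* in both groups, and no true migraine difference.
- Assumed ranges: share gap 10 to 30 points, *d* from 0.2 to 0.5 SD.

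**Shift of the undivided contrast**

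With infected shares p_M (migraine) and p_C (controls):

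undivided contrast = migraine contrast + (p_M − p_C) × d

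The second term is zero if the shares are equal or if d is zero.

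**Rejection rate**

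SE = √{[2 + p_M(1 − p_M)d² + p_C(1 − p_C)d²] / 75}, and with k = shift / SE, the rate is Φ(−1.96 + k) + Φ(−1.96 − k).

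- 10-point gap (55% v 45%), d = 0.2: shift 0.10 × 0.2 = 0.02; SE = √[(2 + 2 × 0.2475 × 0.04)/75] = 0.164; k = 0.122; rate 5.2%.
- 30-point gap (65% v 35%), d = 0.5: shift 0.30 × 0.5 = 0.15; SE = √[(2 + 2 × 0.2275 × 0.25)/75] = 0.168; k = 0.894; rate 14.5%.

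| Share gap | d = 0.2 SD | d = 0.5 SD |
|---|---|---|
| 10 points | 0.02 SD, 5.2% | 0.05 SD, 6.0% |
| 20 points | 0.04 SD, 5.7% | 0.10 SD, 9.1% |
| 30 points | 0.06 SD, 6.5% | 0.15 SD, 14.5% |

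For scale, the difference detectable with 80% power and 75 per group is (1.960 + 0.842) × √(2/75) = 0.457 SD. The shifts of 0.02 and 0.15 SD are 4% and 33% of that.

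**What one stratum gives.** With an even split (assumed), each cell has 37.5 children. The SE of a migraine-control contrast in one stratum is √(2/37.5) = 0.231 SD, and the detectable difference is 2.802 × 0.231 = 0.647 SD.

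**What combining the strata costs.** With assumed shares of 60% and 40%, the cells are 45 and 30 infected, 30 and 45 not infected. Each stratum has variance 1/45 + 1/30 = 0.0556. The equally weighted average has SE √(0.0556/2) = 0.167 SD, against √(2/75) = 0.163 SD for the undivided contrast with the same within-cell SD. The shift from unequal shares is then zero, provided there is no other confounding.

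**The case against.** A reader might infer that the plan ignores COVID-19, and that any difference in infected share is counted as an effect of migraine. The documents do not support that reading, for these reasons:

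- The same paragraph goes on to compare the divided groups within and between each other, and hypothesis 2 repeats this. Migraine against control within each stratum is therefore available. What is missing is only the combined estimate.
- The undivided step names EF only. It is hypothesis 1 that extends the contrast to four domains.
- Hypothesis 1 is worded as a difference between groups, not as an effect of migraine. As a description, an undivided contrast is legitimate and should stay.
- At least some controls attend the same clinic as the cases, so wholly separate recruitment routes cannot be claimed.
- A chance difference in share is already covered by the SE. Only a systematic one biases the contrast.
- The formula needs one COVID-19 effect common to both groups, and hypothesis 2 states none for controls. If controls had no such effect, their infected share would not matter.

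It can also be said that covariates are usually left to a statistical analysis plan, which is not at hand. That stands: the absence of a model is no error in the Protocol. The point rests on the sequence the Protocol does describe, and on its treating COVID-19 status as relevant to the same outcomes.

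**Conclusion.** The point holds as a modest one. The Protocol describes an undivided migraine-control comparison in two non-randomised groups, and neither hypothesis 1 nor the subgroup comparisons yield one estimate that accounts for COVID-19 status. Under the assumptions above, the possible shift runs from 0.02 SD (rejection rate about 5.2%) to 0.15 SD (about 15%). The upper end needs both a systematic 30-point gap and a 0.5 SD effect, and the Protocol shows neither. It would be wrong to conclude that the hypothesis 1 test has an inflated error rate. The most that can be said is that it is unprotected against one imbalance that the study itself measures.

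**What to change.** Tabulate the infected share in each group. For each of the four hypothesis 1 domains, report the migraine-control contrast adjusted for recorded COVID-19 infection, or standardised over it with the same weights in both groups, beside the unadjusted contrast. If the effect of infection appears to differ between the groups, state the weights, because the standardised result then depends on them.

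Use recorded infection only. The Protocol does not define being affected by COVID-19. A broader meaning, such as the impact of restrictions, could itself be influenced by migraine, and adjusting for it could remove part of the difference of interest.

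Matching controls on infection is not proposed: much of the text is in the past tense, so recruitment may be closed.

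The cost is a sentence in the analysis section, one extra table row, about one degree of freedom and a very small loss of precision (SE 0.167 against 0.163 SD in the example). No new data are needed.

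### The correlations (hypothesis 3) and the QOL prediction (hypothesis 4) are specified without COVID-19 status, which hypothesis 2 expects to shift three of the four predictors and QOL in the same children

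*Protocol*

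**What the plan says.** The protocol names the predictors of QOL twice, and the two lists agree. The analysis paragraph before Research Objective says: "Based on the correlations results, we examined whether EF, anxiety, migraine severity and participation predicted QOL". Hypothesis 4 says: "EF, anxiety, migraine severity and participation would significantly predict QOL". Hypothesis 3, also within the migraine group, expects that "significant correlations would be found between migraine severity (Ped MIDAS), EF, anxiety, participation and QOL". None of these mentions COVID-19 status.

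Hypothesis 2 expects that "children with migraine who were affected by COVID-19 would have the lowest EF, highest anxiety, lowest participation and QOL". The comparison is both within and between groups, so it includes affected against unaffected children with migraine. Migraine severity is not among the variables it names.

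The Health status questionnaire, given to all participants, collects COVID-19 information, "as whether the child was infected by the virus". The stated aim is to "explore COVID-19 pandemic on the executive functions (EF) , and quality of life of children with migraine" and in healthy controls.

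**The concern.** Hypotheses 2, 3 and 4 use the same children with migraine. If affected children score worse on EF, anxiety, participation and QOL together, pooling them with unaffected children makes these scores move together even where they have no link of their own. All the expected shifts are adverse, so the pooled correlations are pushed in the direction that hypothesis 3 predicts.

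In the QOL model, what is at stake is the reading of a coefficient. Without a COVID-19 term, the finding that anxiety contributes to QOL cannot be told apart from the finding that affected children are both more anxious and lower in QOL, unless COVID-19 acts on QOL only through the listed predictors. If the correlations also decide which predictors enter the model, as the analysis paragraph may mean, the shared COVID-19 variation enters that choice too.

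**Working it through.** The protocol gives no significance level, effect size, standard deviation or COVID-19 prevalence, so there is no stated figure to reproduce.

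**Inputs from the protocol.** n = 75 children with migraine (Study Population). Hypothesis 2 names three of the four predictors, and QOL. With one score per construct, hypothesis 3 has 5 × 4 / 2 = 10 pairs, of which 4 × 3 / 2 = 6 join variables named in hypothesis 2.

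**Assumptions.** Two-sided 5% level. Share affected p = 0.3 or 0.5. The same shift d (in within-status SDs) in EF, anxiety, participation and QOL. No other link between any of these scores.

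**Step 1, correlations.** Write k = p(1−p)d². COVID-19 status alone induces r = k/(1 + k). At p = 0.5 and d = 0.8, k = 0.25 × 0.64 = 0.16 and r = 0.16/1.16 = 0.138. The chance of significance follows from Fisher z: atanh(0.138) × √72 = 1.18, so about 22%. With n = 75 an observed correlation is significant from |r| = 0.227.

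**Step 2, regression coefficients.** With three equally shifted predictors and migraine severity unshifted, the slope induced on each shifted predictor is k/(1 + 3k). At p = 0.5 and d = 0.8 this is 0.16/1.48 = 0.108. Rejection rates come from simulation (4,000 runs per setting).

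| d | Induced r (p = 0.3; 0.5) | False positives per correlation | Induced slope (p = 0.3; 0.5) | False positives per coefficient |
|---|---|---|---|---|
| 0.3 | 0.02; 0.02 | 5% | 0.02; 0.02 | 5% |
| 0.5 | 0.05; 0.06 | 7% to 8% | 0.05; 0.05 | 7% |
| 0.8 | 0.12; 0.14 | 17% to 22% | 0.10; 0.11 | 13% to 15% |
| 1.0 | 0.17; 0.20 | 32% to 41% | 0.13; 0.14 | 19% to 23% |

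The overall F test of the four predictors rejects 20% to 26% of the time at d = 0.8 and 39% to 50% at d = 1.0. With a COVID-19 term, the joint test of the four predictors rejects 4.5% to 5.1% and the single coefficient 4.8% to 5.3%, in every setting.

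**Step 3, COVID-19 acting only through the predictors.** Let QOL = 0.5 × anxiety + 0.5 × participation + unit noise (scores oriented so that higher is better), with EF shifted by COVID-19 but unrelated to QOL otherwise. QOL then differs by d/√1.5, which is 0.65 SD at d = 0.8 and 0.82 SD at d = 1.0, so hypothesis 2 is true. In simulation the unadjusted coefficients are unbiased (0.50 against a true 0.50), and the null EF coefficient rejects at about 5%. The raw EF–QOL correlation still carries COVID-19 variation: r = k/√((1 + k)(1.5 + k)). At p = 0.5 and d = 0.8 this is 0.16/√(1.16 × 1.66) = 0.12.

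**Step 4, relation to hypothesis 2.** Power for the COVID-19 difference in QOL within the migraine group is about Φ(d√(75p(1−p)) − 1.96). This is 51% to 58% at d = 0.5 and 89% to 93% at d = 0.8. The effect that this sample can reliably show for hypothesis 2 is about the size at which the distortion becomes material.

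**Step 5, price of the term.** Adding status multiplies the standard error of a shifted predictor by about √(1 + k/(1 + 2k)) when COVID-19 explains nothing further in QOL. At k = 0.25 this is √(1 + 0.25/1.5) = 1.08.

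**The case against.** A reader might infer that, if hypothesis 2 is true, the hypothesis 4 coefficients must be inflated. The documents do not support this. Hypothesis 2 states expected group differences, and these fit a COVID-19 effect that runs entirely through anxiety and participation; step 3 shows no bias in that case. The objection stands for hypothesis 4 but not for the raw correlations of hypothesis 3.

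A reader might also infer that COVID-19 is a common cause of every predictor. Hypothesis 2 does not name migraine severity. The Background says that pandemic conditions "have raised concerns about the potential amplification in frequency and severity of childhood migraines", but that concerns the pandemic in general and not affected against unaffected children. The protocol nowhere calls COVID-19 status a cause of the scores.

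Hypothesis 4 is worded as prediction, and omitting a covariate does not falsify a prediction. This stands: harm arises only when coefficients are read as separate contributions.

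The effect of COVID-19 on QOL is examined under hypothesis 2, so the study is not silent on it. This also stands.

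Finally, covariates are commonly left to a statistical analysis plan, which is not shown, and the protocol excludes none. The point is therefore a comment on the predictor set that the protocol states, and not evidence that no adjustment will be made.

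**Conclusion.** The point holds in a limited form. The stated variables for hypotheses 3 and 4 leave out a factor that hypothesis 2 expects to move three of the four predictors and the outcome in the same children. If that expectation is right, the raw correlations among EF, anxiety, participation and QOL (six of the ten pairs) carry some COVID-19 variation. The QOL coefficients are biased only as far as COVID-19 affects QOL outside the listed predictors.

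The size depends on quantities that the protocol does not give. The distortion is negligible at d = 0.3, small at d = 0.5 and material from about d = 0.8. The rates in the table are for the unfavourable case in which the scores share nothing but COVID-19 status; correlation among the predictors within status groups would change the coefficient rates. The correlation rates should not be quoted for hypothesis 4, where the rates per coefficient are clearly lower at d = 0.8 and above. Because the protection is cheap and the status is already collected, the change is worth making.

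**What to change.** Add COVID-19 status as a covariate in the hypothesis 4 model. Base any statement about the separate contribution of EF, anxiety or participation on the adjusted coefficients. For hypothesis 3, report partial correlations given COVID-19 status beside the raw correlations.

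The covariate must be defined exactly as for hypothesis 2. The protocol speaks of being affected, of infection and of restrictions, so it should first say which of these forms the groups.

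The cost is one degree of freedom and a line of text, with no new data. With one score per construct the model has five terms for 75 children, or 15 children per term; using several BRIEF or STAIC scores would lower that ratio. Standard errors of the shifted predictors widen by up to about 8% (step 5), and by less where COVID-19 also explains QOL directly.
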